# 3 LIST OF ABBREVIATIONS

Abbreviation	Definition
AE	Adverse Event
ATC	Anatomical Therapeutic Chemical
BMI	Body Mass Index
COVID-19	Coronavirus Disease of 2019
CSR	Clinical Study Report
ECOG	Eastern Cooperative Oncology Group
eCRF	electronic Case Report Form
FAS	Full Analysis Set
HCG	Human Chorionic Gonadotropin
ICH	International Council for Harmonisation
IEAS	Imaging Evaluable Analysis Set
IMP	Investigational Medicinal Product
LITT	Laser Interstitial Thermal Therapy
MedDRA	Medical Dictionary for Regulatory Activities
MRI	Magnetic Resonance Imaging
NCI-CTCAE	National Cancer Institute Common Terminology Criteria for
	Adverse Events
NPV	Negative Predictive Value
PET	Positron Emission Tomography
PPV	Positive Predictive Value
PT	Preferred Term
ROC	Receiver Operating Characteristic
SAE	Serious Adverse Event
SAF	Safety Analysis Set
SAP	Statistical Analysis Plan
SAS	Statistical Analysis Software
SoC	Standard of Care
SOC	System Organ Class
SoT	Standard of Truth
SUV	Standardized Uptake Value
$SUV_{max}$	Maximum Standardized Uptake Value
$SUV_{peak}$	Peak Standardized Uptake Value
$SUV_{mean}$	Mean Standardized Uptake Value
TAC	Time Activity Curve
TBR	Tumor Background Ratio
$TBR_{max}$	Maximum Tumor to Background Ratio
$TBR_{peak}$	Peak Tumor to Background Ratio
TEAE	Treatment-Emergent Adverse Event
TESAE	Treatment-Emergent Serious Adverse Event
WHODrug	World Health Organization Drug Dictionary

Confidential Page 4 of 22

### 4 INTRODUCTION

The purpose of this statistical analysis plan (SAP) is to provide comprehensive and detailed descriptions of the methods and presentation of data analyses proposed for Blue Earth Diagnostics Protocol BED-FLC-219 (An Open-label, Single-arm, Single-dose, Prospective, Multicenter Phase 2b Study to Establish Image Interpretation Criteria for F-fluciclovine Positron Emission Tomography (PET) in Detecting Recurrent Brain Metastases After Radiation Therapy (PURSUE)). Descriptions of planned analyses are provided in order to avoid post hoc decisions that may affect the interpretation of the statistical analysis. The statistical methods applied in the design and planned analyses of this study are consistent with the International Council for Harmonisation (ICH) guideline *Statistical Principles for Clinical Trials* (E9) (1998).

This SAP will be finalized prior to data analysis to provide full details, including templates for tables, listings, and figures, to be presented in the clinical study report (CSR). Any changes between the statistical methods provided in the clinical study protocol and this SAP will be explained herein; any changes or deviations from this SAP relative to the final analysis will be fully documented in the CSR. Minor changes or deviations from the templates for tables, figures, and listings need not be documented in the CSR.

#### 5 STUDY OBJECTIVES

### 5.1 Primary Study Objective

The primary objective of this study is

• To establish visual image interpretation criteria for F-fluciclovine PET in detecting recurrent brain metastases.

### 5.2 Secondary Study Objectives

The secondary objectives of this study are:

- To establish other image interpretation criteria for F-fluciclovine PET in detecting recurrent brain metastases.
- To assess subject-level diagnostic performance of F-fluciclovine PET in detecting recurrent brain metastases.
- To assess lesion-level diagnostic performance of F-fluciclovine PET in detecting recurrent brain metastases.
- To assess the safety of F-fluciclovine injection in the subject population.

#### **6 INVESTIGATIONAL PLAN**

#### 6.1 Overall Study Design

This is a prospective, open label, single arm, single dose study in subjects with solid tumor brain metastases previously treated with radiation therapy, designed to define

Confidential Page 5 of 22

image interpretation criteria for F-fluciclovine PET in detecting recurrent brain metastases (when read with standard magnetic resonance imaging (MRI) for anatomical reference).

Subjects with a history of brain metastases previously treated with primary, adjuvant or repeat (salvage) radiation therapy, with a recent standard of care (SoC) brain MRI found to be equivocal for recurrent brain metastasis, and who meet all inclusion criteria and none of the exclusion criteria, will be consented and enrolled. Sites are encouraged to enroll subjects with a variety of primary tumor types. In order to ensure variation in tumor types on the study population, the number of subjects with lung cancer will be capped at approximately 60% of enrolled subjects.

On-site investigators will prospectively annotate and measure the 'reference lesion' on a post-radiation treatment MRI scan and on the SoC MRI brain scan to confirm eligibility. The 'reference lesion' is defined as the lesion which is:

- equivocal for recurrent metastasis on SoC MRI (according to inclusion criterion #7, protocol section 6.2);
- intended for pre-planned SoC craniotomy; and
- if >1 equivocal lesion is intended for resection, the largest of these lesions.

If >1 equivocal lesion is intended for resection, the on-site investigator will also annotate and measure the other lesions (termed 'MRI surgical lesions') on the SoC MRI brain scan, defined by the same radiological criteria for a reference lesion per inclusion criterion #7 (see protocol section 6.2).

All eligible subjects will receive an F-fluciclovine PET scan (Visit 2 PET) within 42 days of SoC MRI. Subjects will then undergo a repeat study-specific brain MRI scan (Visit 2 On-Study MRI) to be used as anatomical reference for the F-fluciclovine PET scan. The Visit 2 On-Study MRI should be done ideally on the same day, otherwise ≤3 days after Visit 2 PET and completed before the pre-planned SoC craniotomy. A safety follow-up (Visit 3) 1 to 3 days after Visit 2 PET will be made for adverse event (AE) evaluation by telephone call or in person (if same day as scheduled SoC craniotomy). AEs occurring from the time of F-fluciclovine administration until 1 day post F-fluciclovine administration will be recorded. The safety follow-up must be completed before the pre-planned SoC craniotomy. The Visit 2 PET must be organized to take place a minimum of 1 day and maximum of 21 days before pre-planned SoC craniotomy.

The on-site investigator will review the F-fluciclovine PET scan to identify, annotate and measure potential additional lesions, not previously reported on SoC MRI (termed 'additional PET lesions'). Additional PET lesions should be annotated only where judged suggestive of brain metastasis, warranting confirmation according to SoC practice, be neurosurgically feasible and accordingly, planned for biopsy or resection. Undertaking biopsy / resection of additional PET lesion(s) identified on the F-fluciclovine PET scan is at the discretion of on-site investigators. Moreover, an additional PET lesion should be discrete and spatially separate from known, pre-existing lesions. In particular, the following should not be annotated as Additional PET lesions: known pre-existing non-progressive lesions (considered at site level as

Confidential Page 6 of 22

stable or partially responding), F-fluciclovine activity contiguous with a known lesion (previously annotated or otherwise) and apparently incongruent with the

lesion's outline on correlating MRI, particularly where this may be reasonably explained by image registration.

For each subject, the final visit will usually be the preplanned SoC craniotomy/surgery at Visit 4. The subject will receive post-procedural management per institutional SoC. All ongoing follow-up and any further treatment will be in accordance with SoC and will not be recorded, including all medications and SoC procedure-related events occurring at and beyond Visit 4, and any SoC follow-up.

Subject-level standard of truth (SoT) will be defined by central histopathological diagnosis of the reference lesion. Lesion-level SoT will be defined by central histopathological diagnosis of all sampled lesions (reference lesions, MRI surgical lesions, additional PET lesions). Separately, central image analysis will define qualitative and quantitative lesion uptake of F-fluciclovine, for each resected lesion. These results will be reviewed by an Imaging Interpretation Committee to form image interpretation criteria.

#### Concurrent Enrollment with BED-FLC-312

Subjects who are enrolled in BED-FLC-312 and during its Follow-Up period are deemed to require a SoC craniotomy for diagnostic evaluation of an equivocal lesion, may be enrolled into BED-FLC-219 while remaining enrolled in BED-FLC-312. Subjects may be enrolled any time during the BED-FLC-312 Follow-Up period after Day 22 (i.e., after the full 21-day maximum timeframe for completion of the BED-FLC-312 Visit 4 neurosurgical procedure). For absolute clarity, this will be irrespective of the applicability of BED-FLC-312 Visit 4 to the subject. Such subjects will be required to sign an informed consent form and meet all eligibility requirements for BED-FLC-219, including availability of the SoC MRI within the specified timeframe and reference lesion definitions. All BED-FLC-219 procedures remain applicable to any such concurrently enrolled subjects. Interim enrollment in BED-FLC-219 does not impact the subject's subsequent ongoing participation in BED-FLC-312.

Confidential Page 7 of 22

#### 6.2 **Schedule of Assessments**

	Day -42 to -1 SoC MRI	Visit 1 Day -28 to -1 Screening	Visit 2 Day 1 IMP + PET	Visit 2 Day 1 to 4 On-Study MRI	Visit 3  Day 2 to 4  Safety Follow-Up Phone Call	Visit 4 Day 2 to 22 SoC Craniotomy
	Before Visit I	creening 2 Day I	1 to 21 days before SoC craniotomy/surger y Visit 4 Day 3	Day of  Day of  F-fluciclovine injection or up to 3 days after	I to 3 days after  F-fluciclevine injection, before SoC Craniotomy	At time of pre-planned SoC craniotomy/surgery and after Visit 2 MRI and Visit 3 Follow-Up
SoC MRI	X		1000	12-22		- 23
Informed Consent		X				
Confirm inclusion/exclusion criteria		x				
Demographics *		X				
Baseline Characteristics b			Х			
Medical / Disease History *		X	X			
ECOG Performance Status 4		X				
Concomitant Medications		X	X		X	
Vital Signs*			X			
Pregnancy Test (Urine)		X	X			
Order "F-fluciclovine dose		X				
Eligibility Review #		X	X			
"F-fluciclovine Injection		1000	X			
18F-fluciclovine PET Brain Scan			x			
Adverse Events			X		X	
On-Study MRI Brain Scan			1000	X	3 200	
Annotate Reference Lesion on SoC MRI Brain Scan		X				
Annotate MRI surgical lesions (i.e. other lesions intended for resection per SoC [if applicable])		X				
Identify and annotate additional PET lesions (i.e. potential additional lesions not previously reported on SoC MRI [if applicable]) 				x		
Confirm sites of reference lesion and MRI surgical lesions on Visit 2 scans				x		

	Duy -42 to -1 SoC MRI Before Visit 1 Screening	SoC MRI Screening IMP + PET  1 to 21 days Within 28 to 1 before SoC Before Visit 1 days before Visit craniotomy/surger	Day 1	Visit 2 Day 1 to 4 On-Study MRI	Visit 3 Day 2 to 4 Sufety Follow-Up Phone Call	Visit 4 Day 2 to 22 SoC Craniotomy
			Day of  inf-fluciclovine injection or up to 3 days after	1 to 3 days after  18F-fluciclovine injection, before SoC Craniotomy	At time of pre-planned SoC craniotomy/surgery and after Visit 2 MRI and Visit 3 Follow-Up	
Safety Follow-up Phone Call					X	
SoC Craniotomy/Surgery	Ī				7,70	X
Record sites of all sampled lesions						х
Document Neurosurgical Procedure						х
Record local histopathology results and send specimens to central histopathology laboratory					10	X

ECOG, Eastern Cooperative Oncology Group; IMP, investigational medicinal product; MRI, magnetic resonance imaging; PET, positron emission tomography; SoC,

#### 6.3 Treatment(s)

#### 6.3.1 Treatment(s) Administered

Subjects will receive a single dose of F-fluciclovine by injection, 185 MBq (5 mCi)  $\pm$  20%, delivered as an intravenous bolus by site staff.

#### 6.3.2 Method of Assigning Subjects to Treatment Groups

Not applicable. All subjects will receive a single dose of F-fluciclovine.

Confidential Page 8 of 22

\*\*Standard of care.\*\*

\*\*Demographic information recorded at Screening will include age, sex, race and ethnicity.

\*\*Baseline assessments will include pre-scan body weight and height.

\*\*Treatment history for previous cancer to include previous treatments for brain metastases and previous cancer treatments for primary tumor

\*\*A standard of care ECOG assessment may be recorded as the Screening ECOG if the assessment was performed within 28 days of Screening.

\*\*Vital signs (body temperature, blood pressure, pulse and respirations) will be collected after resting for at least 5 minutes before IMP injection, and after resting for at least 5 minutes following PET scan.

Females of child-bearing potential.

Eligibility review to include collection and review of prior pre- and post-treatment MRI brain scans as needed to confirm eligibility. Prior pre- and post-treatment MRI brain

seans and current SoC MRI images to be uploaded to central imaging core lab.

Additional PET lesions' are potential additional lesions identified by the on-site investigator on F-fluciclovine PET scan (with Visit 2 MRI for anatomical reference), not previously reported on SoC MRI, should be judged suggestive of brain metastasis, warranting confirmation according to SoC practice, and be neurosurgically feasible and accordingly, planned for biopsy / resection.

#### 6.4 Efficacy and Safety Variables

### 6.4.1 Efficacy Variable(s)

# 6.4.1.1 Primary Efficacy Variable

The primary efficacy endpoint is:

• Diagnostic performance (sensitivity, specificity, positive predictive value [PPV] and negative predictive value [NPV]) of different thresholds of lesion F-fluciclovine uptake on visual reads (as defined by the different combinations of degree of uptake) versus SoT derived from central histopathological analysis of all lesions, at subject-level and lesion-level.

F-fluciclovine uptake of all sampled lesions, including the reference lesion, will be determined from static imaging data (e.g., from 10-20 minutes post-injection), using the following definitions:

- Absent F-fluciclovine uptake indistinguishable from surrounding structurally normal brain parenchyma
- Mild F-fluciclovine uptake above surrounding structurally normal brain parenchyma, up to or similar to blood pool in the venous sinuses
- Moderate F-fluciclovine uptake higher than blood pool, up to or similar to parotid glands (if parotid gland uptake is asymmetrical, uptake in the gland with higher uptake is used as reference).
- Marked F-fluciclovine uptake higher than parotid glands.

Three thresholds of lesion F-fluciclovine uptake, derived from visual reads in the 3 independent reader evaluation, will be considered:

Threshold	Combination of degree of uptake		
Mild or higher uptake	Absent uptake vs (Mild + Moderate + Marked uptake)		
Moderate or higher uptake	(Absent + Mild uptake) vs (Moderate + Marked uptake)		
Marked uptake	(Absent + Mild + Moderate uptake) vs Marked uptake		

For each threshold, a 2x2 table will be created for each reader at subject level and also at lesion level.

	Tumor Present (SoT) Tumor Absent	
Threshold Met	True positive	False positive
Threshold Not Met	False negative	True negative

Sensitivity, specificity, PPV and NPV for each threshold will be calculated using standard definitions:

• Sensitivity (% of true positives) = true positive / (true positive + false negative)

Confidential Page 9 of 22

- Specificity (% of true negatives) = true negative / (true negative + false positive)
- PPV = true positive / (true positive + false positive)
- NPV = true negative / (true negative + false negative)

Subject-level diagnostic performance will be calculated based on reference lesion data, while lesion-level diagnostic performance will be calculated based on data of all sampled lesions.

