#### 7.4.3 Primary Efficacy Endpoint Analysis Methods

For each uptake threshold (Mild or Higher Uptake, Moderate or Higher Uptake, Marked Uptake), the number and percentage of True Positives, False Positives, True Negatives, and False Negatives will be presented for each reader. Sensitivity, Specificity, PPV and NPV will be calculated, with estimates and the 95% exact confidence intervals displayed.

The summary will be presented for subject-level performance (based on reference lesion data), and repeated for lesion-level performance (based on data of all sampled lesions).

For lesion-level performance, confidence intervals will be calculated based on the methodology described by Zhou et al., to account for clustering within subjects. The formula for PPV is:

$$\widehat{PPV} = \sum_{P} TP_{p} / \sum_{P} Pos_{p}$$

$$\widehat{Var}(\widehat{PPV}) = \frac{1}{P(P-1)} \sum_{P} \binom{Pos_{p}}{Pos}^{2} (\widehat{PPV_{p}} - \widehat{PPV})^{2}$$

With:

 $\boldsymbol{P}$ : (number of) Patients

 $\begin{array}{ll} p & : \text{ individual patient} \\ Pos_p & : \text{ Number of positive regions for patient } p \\ \hline Pos & : \text{ Number of true positive regions for patient } p \\ \hline Pos & : \text{ Number of true positive regions for patient } p \\ \hline Pos & : \text{ Mean cluster size} \end{array}$ 

 $\widehat{PPV_p} = TP_p/Pos_p$ : Patient PPV

The example in Zhou et al. is coded in SAS in Appendix 1.

In addition, pairwise inter-rater agreements at the lesion level for the 3 readers will be tabulated for the F-fluciclovine uptake. The proportions of agreement vs disagreement, Cohen's Kappa and the associated 95% confidence interval will be calculated.

Confidential Page 16 of 22 The results of these analyses will be reviewed by the separate Image Interpretation Committee as described in the study protocol to determine image interpretation criteria based on visual reads.

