# 7.4.4 Secondary Endpoint Analysis Methods

In order to establish other image interpretation criteria for  $^{18}\text{F}$ -fluciclovine PET in detecting recurrent brain metastases, receiver operating characteristic (ROC) analysis of SoT against the quantitative measures of lesion  $^{18}\text{F}$ -fluciclovine uptake will be performed for each reader. A ROC curve will be produced for lesion SUV $_{\text{max}}$ , SUV $_{\text{peak}}$ , TBR $_{\text{max}}$  and TBR $_{\text{peak}}$ , with each point corresponding to a specific threshold, eg.  $\geq$  SUV $_{\text{max}}$  value vs < SUV $_{\text{max}}$  value. The AUC of each curve will be calculated using the trapezoidal method and will be annotated on the plot. Sensitivity, specificity, PPV, and NPV will be listed for each value of lesion SUV $_{\text{max}}$ , SUV $_{\text{peak}}$ , TBR $_{\text{max}}$  and TBR $_{\text{peak}}$ .

For TBRmax and TBRpeak, pairwise inter-rater agreement will be assessed using Pearson correlation coefficients.

For dynamic measures of lesion F-fluciclovine uptake represented by TAC type, applying each TAC category as a diagnostic criterion, estimates and the 95% exact confidence intervals for sensitivity, specificity, PPV and NPV for each of the 4 TAC types will be calculated and presented, by reader, on both subject and lesion levels. Lesion-level confidence intervals will be based on the method by Zhou et al..

In addition, pairwise inter-reader agreements at the lesion level for the 3 readers will be tabulated for TAC type. The proportions of agreement vs disagreement, Cohen's Kappa and the associated 95% confidence interval will be calculated.

These analyses will be reviewed by the separate Image Interpretation Committee to determine a set of image interpretation criteria based on the quantitative and dynamic measures.

Subsequently, for the diagnostic performance secondary endpoints, estimates and the 95% exact confidence intervals for sensitivity, specificity, PPV and NPV will be calculated based on the recommended thresholds from the following combination of interpretation criteria (if featured in the interpretation criteria):

- 1. Visual assessment of level of lesion F-fluciclovine uptake
- 2. Strongest performing quantitative measure (based on ROC analysis)

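### Lesion-level results pool MRI-selected lesions with lesions sampled because the on-site PET read was suggestive, and no planned lesion-level table separates the two groups

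*SAP*

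**What the plan says.** Section 6.1 sets two routes by which a lesion reaches histology.

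- **MRI route.** The reference lesion, and any MRI surgical lesions, are equivocal on the standard-of-care MRI and already intended for resection before the study PET is done.
- **PET route.** The on-site investigator looks on the study PET for lesions that the standard-of-care MRI did not report. The rule is: "Additional PET lesions should be annotated only where judged suggestive of brain metastasis, warranting confirmation according to SoC practice". Whether they are then biopsied or resected "is at the discretion of on-site investigators". A footnote to the schedule of assessments (Section 6.2) repeats the condition: "not previously reported on SoC MRI, should be judged suggestive of brain metastasis".

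Both routes feed one analysis. Section 6.1: "Lesion-level SoT will be defined by central histopathological diagnosis of all sampled lesions (reference lesions, MRI surgical lesions, additional PET lesions". Section 6.4.1.1: "lesion-level diagnostic performance will be calculated based on data of all sampled lesions". Section 7.4.3 says the primary summary is "repeated for lesion-level performance (based on data of all sampled lesions". In Section 6.4.1.2 the quantitative, dynamic and combined-criteria endpoints are also lesion-level as well as subject-level. Section 7.4.4 restates the lesion level only for time activity curve (TAC) type: "by reader, on both subject and lesion levels".

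Subject-level performance uses the reference lesion alone (Sections 6.4.1.1 and 7.4.3). The lesion-level subgroups in Section 7.4.5.5 are primary tumor type and concurrent immunotherapy; none is by lesion class.

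**The concern.** An additional PET lesion is in the data set because the index test looked suggestive there. By that route, a location that did not look suggestive on PET is never sampled. The class can therefore be expected to supply mainly true and false positives, and few false or true negatives, at a low uptake threshold.

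Sensitivity and specificity from the pooled set then depend partly on how many such lesions sites chose to sample. The clustered variance in Section 7.4.3 allows for correlation within a subject, not for how a lesion entered the sample. The Image Interpretation Committee forms the reading criteria from these tables. If lesion-level and subject-level results differ, the planned tables cannot show whether the MRI surgical lesions or the PET-selected lesions caused the difference.

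**Working it through.** **No SAP figure to reproduce.** The SAP gives no expected number of additional PET lesions and no expected accuracy. Section 7.6 gives only up to 40 subjects, without a formal calculation. All counts below are assumptions.

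**Formulas.** Let MRI-selected lesions have counts TP, FN, FP, TN, with sensitivity Se0 and specificity Sp0. Add t tumor and b non-tumor additional PET lesions. A central reader calls a share c_T of the tumor additions and c_B of the non-tumor additions positive.

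- Pooled sensitivity = (TP + t·c_T) / (TP + FN + t), above Se0 only if c_T > Se0.
- Pooled specificity = (TN + b·(1 − c_B)) / (TN + FP + b), below Sp0 only if c_B > 1 − Sp0.

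The comparison is thus with the positivity rate of MRI-selected lesions in the same standard-of-truth class.

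**Mild or higher, every addition confirmed (c_T = c_B = 1).** Assume 25 tumor and 20 non-tumor MRI-selected lesions.

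| Base Se0 / Sp0 (TP, FN, FP, TN) | t, b | Sensitivity | Specificity | PPV |
|---|---|---|---|---|
| 80 / 80 (20, 5, 4, 16) | 0, 0 | 20/25 = 80.0% | 16/20 = 80.0% | 20/24 = 83.3% |
| | 1, 1 | 21/26 = 80.8% | 16/21 = 76.2% | 21/26 = 80.8% |
| | 2, 2 | 22/27 = 81.5% | 16/22 = 72.7% | 22/28 = 78.6% |
| | 0, 4 | 20/25 = 80.0% | 16/24 = 66.7% | 20/28 = 71.4% |
| 80 / 50 (20, 5, 10, 10) | 0, 0 | 20/25 = 80.0% | 10/20 = 50.0% | 20/30 = 66.7% |
| | 2, 2 | 22/27 = 81.5% | 10/22 = 45.5% | 22/34 = 64.7% |

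NPV = TN/(TN + FN) does not change in any row. If all four additions are tumor, specificity does not move.

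**A second set of assumptions.** Take 40 MRI-selected lesions, 60% tumor, Se0 80%, Sp0 70%, and four additions of which 50–80% are tumor and 90–100% are confirmed. Pooled sensitivity is 81–82% and specificity 62–67%.

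**Readers who do not confirm.** From the 80 / 80 base:
- With t = b = 2 and one tumor addition graded Absent, sensitivity is 21/27 = 77.8%, below its base.
- With t = b = 1 and the non-tumor addition graded Absent, specificity is 17/21 = 81.0%, above its base.

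**Moderate or higher.** Assume a base of 60 / 90 (15, 10, 2, 18) and t = b = 2.
- None reach Moderate: 15/27 = 55.6% and 20/22 = 90.9%.
- One of each does: 16/27 = 59.3% and 19/22 = 86.4%.
- All do: 17/27 = 63.0% and 18/22 = 81.8%.

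The direction is not fixed.

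**Scale of sampling error.** The exact 95% interval for 16/20, treating lesions as independent, is 56.3% to 94.3%. Every shift above lies inside it or is small beside its width.

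**The case against.** The strongest reply is that nothing here is an error. The SAP is consistent in defining lesion level as all sampled lesions, and the study tests no hypothesis. That stands: a reader might infer that the endpoint is wrongly defined or contradicts itself, and the SAP does not support that reading.

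A reader might also infer that pooling inflates sensitivity and depresses specificity throughout. The SAP does not support this either. The table grades are "derived from visual reads in the 3 independent reader evaluation" (Section 6.4.1.1), so the on-site read does not fix them. The direction follows only at Mild or higher, and only if those readers confirm the uptake often enough.

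The effect may also be nil. Section 6.1 restricts additional PET lesions tightly: they must be suggestive, surgically feasible, planned for sampling, and discrete from known lesions. Zero or very few among up to 40 subjects is plausible.

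The overlap argument also has force. Subject-level tables already give an estimate free of PET selection. In the 45-lesion illustration, 40 subjects would put 40 of those lesions in the subject-level table, so a restricted lesion-level table might add only 45 − 40 = 5.

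Finally, subject listings should generally hold the data (Section 7.1.1). But a split made after results are seen is the kind of post hoc decision that Section 4 aims to avoid. Independent grading does not undo selection into the sample, and more subjects would not remove it.

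**Conclusion.** The point holds as a modest one. Part of the primary endpoint mixes lesions chosen on MRI with lesions chosen on the index test, the mix depends on site discretion, and no planned lesion-level table or subgroup shows the two apart.

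At Mild or higher, with one or two additions of each histology, all confirmed, and an 80 / 80 base, sensitivity rises by 0.8 to 1.5 points and specificity falls by 3.8 to 7.3 points. These sizes rest on assumed counts and full reader confirmation. They are within sampling error, and they vanish if no additional PET lesion is sampled. At the higher thresholds, and for TAC and quantitative measures, results can depend on these lesions in either direction. Subject-level results are unaffected.

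**What to change.** Keep the pooled lesion-level result as defined, and add the following.

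1. **Section 7.4.3:** a supplementary lesion-level table of sensitivity, specificity, PPV and NPV for the three visual thresholds, restricted to reference and MRI surgical lesions.
2. **Section 7.4.4:** the same restriction for the lesion-level TAC and final combined-criteria results. Repeat the ROC analyses only if additional PET lesions were sampled.
3. **Additional PET lesions:** report them separately by count, histology and per-reader PPV.
4. **One sentence** stating that pooled lesion-level sensitivity and specificity include lesions selected on the index test.

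The Section 7.4.5.5 subgroups need no split. If the protocol does not describe the restricted tables, list them in Section 7.7 as added supplementary analyses.

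The cost is small. Sites already annotate lesion class, and Section 7.3.3 already counts reference and MRI surgical lesions together, so this is a filter. The downside is a few more tables, repeated by reader, with slightly smaller denominators.
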